**Statistical Analysis Plan:**

2.0 / 09-Jun-2023

**PROGRAMMING NOTES:**

- Present all groups from Part A in separate figures and one figure with all patients.
- Use a different color style for each BOR separately (CR/PR/SD/PD/NE).
- Add reference lines for +20% and -30%.

Figure 14.2-1.2.2 – Spider plot of Percentage Change from Baseline in Sum of Longest Diameter  
Per Protocol Set

**PROGRAMMING NOTES:**

- Repeat Figure 14.2-1.2.1
- Present data on Per Protocol Set.

Figure 14.2-1.2.3 – Spider plot of Percentage Change from Baseline in Sum of Longest Diameter  
Evaluable Analysis Set

**PROGRAMMING NOTES:**

[figure not shown]
- Repeat Figure 14.2-1.2.1
- Present data on Evaluable Analysis Set.

BioMed Valley Discoveries  
Protocol: BVD-523-ABC ('Delivery' / 'Type') - Part X  
Data extraction date: DDMMYYYY

Page 1 of Y

Figure 14.2-1.3.1 - Waterfall plot of Maximum Percentage Change from Baseline in Sum of Longest Diameter  
Full Analysis Set

Group = Group X

Maximum percentage change from baseline in total tumor size is the maximum percent change in the sum of longest diameters/short axis for all target lesions observed from baseline for each patient.

Best overall response: CR=Complete Response, PR=Partial Response, SD=Stable Disease, PD=Progression Disease, NE=Not Evaluable.

Program: (Program name.sas) (run on: DDMMYYYY HH:MM)

Filename: (Specify file name.rtf)

**PROGRAMMING NOTES:**

- Present each group from Part A on one figure and one figure with all patients.
- Each bar is an individual patient.
- Add reference lines for +20% and -30%.
- Add the best overall response (CR, PR, SD, PD, NE) of each patient on the top of each bar.

Figure 14.2-1.3.2 – Waterfall plot of Maximum Percentage Decrease from Baseline in Sum of Longest Diameter  
Per Protocol Set

**PROGRAMMING NOTES:**

[figure not shown]
- Repeat Figure 14.2-1.3.1
- Present data on Per Protocol Set.

Figure 14.2-1.3.3 – Waterfall plot of Maximum Percentage Decrease from Baseline in Sum of Longest Diameter  
Evaluable Analysis Set

**PROGRAMMING NOTES:**

- Repeat Figure 14.2-1.3.1
- Present data on Evaluable Analysis Set.

Figure 14.2-1.4.1 - Swimmer Plot of Response Assessments  
 Full Analysis Set

Program: (Program name.sas) (run on: DDMMYYYY HH:MM)

Filename: (Specify file name.rtf)

**PROGRAMMING NOTES:**

- Present each group from Part A on one figure and a figure including all patients.
- Display patient ID on the left outside the figure.
- The bar displays time to PD/Death (PFS), with “PD” or “death” displayed at the end of the bar; if no PD/death occurred before cutoff date, the bar stops at cutoff date.
- For responders, display the date of first CR or PR, and display “Ongoing response” arrow if no PD or death occurred before cutoff date.
- “End of Treatment” is the date of treatment discontinuation, this must be displayed only for patients who discontinued the treatment before the cut-off date.

Figure 14.2-1.4.2 – Swimmer Plot of Response Assessments  
Per Protocol Set

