#### 9.8.2 Duration of Response (DOR)

The duration of response (in months) is defined as the period from the date of initial confirmed PR or CR until the date of first radiographically documented progressive disease or death from any cause. Only patients with BOR of CR or PR (i.e. responders) will be included in the analysis of duration of response.

$$DOR = [(Date of first PD/death - Date of first recorded confirmed CR/PR) + 1] / 30.4375$$

Patients with no documented progression or death after CR or PR will be censored at the last available tumor assessment (last assessment that is CR, PR, or SD):

$$DOR = [(Date of last assessment - Date of first recorded CR/PR) + 1] / 30.4375$$

The analysis of DOR will be performed with a Kaplan-Meier method (product-limit estimates) and a summary of associated statistics will be presented including corresponding two-sided 95% CI. The CI for the median will be calculated according to Brookmeyer and Crowley and CI for the survival function estimates at Month 3, 6, 9, 12, and 18 will be derived using the log-log transformation (SAS PROC LIFETEST CONFTYPE=LOGLOG), only if there are sufficient data for responders. However, the final choice of timepoints may be updated dependent upon the data.

Part B, DOR will be compared between ulixertinib and physician's choice of treatment using a Log Rank test or other appropriate test if the proportional hazards assumption does not hold.

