### 9.8.3 Progression-free Survival (PFS)

The PFS (in months) is defined as the time from the first ulixertinib dose until the first radiographically documented progression of disease or death from any cause, whichever occurs first.

$$PFS = [(Date of first PD/death - Date of first study treatment) + 1] / 30.4375$$

Patients with no documented progression or death will be censored at the last available tumor assessment (last assessment that is CR, PR or SD):

$$PFS = [(Date of last assessment where patient is PD free - Date of first study treatment) + 1] / 30.4375$$

For patients with no post baseline tumor assessment a censored PFS at day 1 will be considered.

$$PFS = (Date of first study treatment - Date of first study treatment) + 1$$

The analysis of PFS will be performed with a Kaplan-Meier method (product-limit estimates) and a summary of associated statistics will be presented including corresponding two-sided 95% CI. The CI for the median will be calculated according to Brookmeyer and Crowley and CI for the survival function estimates at Month 3, 6, 9, 12, and 18 will be derived using the log-log transformation (SAS PROC LIFETEST CONFTYPE=LOGLOG). However, the final choice of timepoints may be updated dependent upon the data.

For Part B, for each histology, PFS curves will be compared between ulixertinib and physician's choice of treatment using Log Rank Test or other appropriate test if the proportional hazards assumption does not hold.

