A & B	Table	14.3-2.6.2	Shift Table of Non-gradable Biochemistry Laboratory Results – Baseline vs Worst On-treatment Value	Safety Set	Analysis	Y
A & B	Table	14.3-2.7	Summary and Change from Baseline in Urinalysis Laboratory Results by Visit	Safety Set	Analysis	
A & B	Table	14.3-3.1	Summary and Change from Baseline in Vital Signs by Visit	Safety Set	Analysis	Y
A & B	Table	14.3-3.2	Shift table of Vital Signs – Baseline vs worst on-treatment value	Safety Set	Analysis	Y
A & B	Table	14.3-3.3	Summary of ECG at Baseline	Safety Set	Analysis	
A & B	Table	14.3-3.4	Summary of ECHO/MUGA at Baseline	Safety Set	Analysis	
A & B	Table	14.3-3.5	Summary of Physical Examination at Baseline	Safety Set	Analysis	
A & B	Table	14.3-3.6	Summary of ECOG Performance Status by Visit	Safety Set	Analysis	
		14.4	Other Efficacy Data			

	14.5		Pharmacokinetic Data		
A	Table	14.5-1.1	Pharmacokinetic Data	Full Analysis Set	Y
A	Table	14.5-1.2	Pharmacokinetic Data	Per Protocol Set	
A	Table	14.5-1.3	Pharmacokinetic Data	Evaluable Analysis Set	
14.6			Blood Pharmacodynamic Data		
A	Table	14.6-1.1	Blood Pharmacodynamic Data	Full Analysis Set	Y
14.2			Figures		
A & B	Figure	14.2-1.1	Consort Diagram	Full Analysis Set	Y
A & B	Figure	14.2-1.2.1	Spider plot of Percentage Change from Baseline in Sum of Longest Diameter	Full Analysis Set	Y
A & B	Figure	14.2-1.2.2	Spider plot of Percentage Change from Baseline in Sum of Longest Diameter	Per Protocol Set	
A & B	Figure	14.2-1.2.3	Spider plot of Percentage Change from Baseline in Sum of Longest Diameter	Evaluable Analysis Set	
A & B	Figure	14.2-1.3.1	Waterfall plot of Maximum Percentage Decrease from Baseline in Sum of Longest Diameter	Full Analysis Set	Y
A & B	Figure	14.2-1.3.2	Waterfall plot of Maximum Percentage Decrease from Baseline in Sum of Longest Diameter	Per Protocol Set	
A & B	Figure	14.2-1.3.3	Waterfall plot of Maximum Percentage Decrease from Baseline in Sum of Longest Diameter	Evaluable Analysis Set	
A & B	Figure	14.2-1.4.1	Swimmer Plot of Response Assessments	Full Analysis Set	Y
A & B	Figure	14.2-1.4.2	Swimmer Plot of Response Assessments	Per Protocol Set	

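### The swimmer plot labels its bar PFS but draws every event-free patient to the data cutoff, with an ongoing-response arrow for responders, contrary to the SAP's own censoring rules

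*SAP*

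**What the plan says.** The notes under Figure 14.2-1.4.1 in the SAP shells define the bar: "The bar displays time to PD/Death (PFS), with" the event type printed at its end. For a patient with neither event, "if no PD/death occurred before cutoff date, the bar stops at cutoff date". Responders have their first CR or PR marked and receive an ongoing-response "arrow if no PD or death occurred before cutoff date". The only other marker is End of Treatment, for those who stopped treatment before cutoff. The notes have no exception or symbol for withdrawal, loss to follow-up, end of study or new anticancer therapy.

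The analysis text differs. On PFS, SAP 9.8.3 says: "Patients with no documented progression or death will be censored at the last available tumor assessment", specified as the last one rated CR, PR or SD. It adds: "For patients with no post baseline tumor assessment a censored PFS at day 1 will be considered". On DOR, SAP 9.8.2 says: "Patients with no documented progression or death after CR or PR will be censored at the last available tumor assessment". Protocol 11.5.5.1 gives the same censoring for both endpoints in Part A.

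In the shells' list of outputs, the full analysis set (FAS) version of the "Swimmer Plot of Response Assessments" is marked for the final analysis. The FAS DOR table (Table 14.2-1.4.1), Kaplan-Meier figure (Figure 14.2-1.5.1) and listing (Listing 16.2.6-5) are not. The PFS table, PFS Kaplan-Meier figure and PFS listing are.

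**The concern.** A swimmer plot may legitimately show time on study. This one is defined as showing PFS, so it should show the PFS that the SAP defines. For an event-free patient it does so only if the last evaluable scan falls on the cutoff date.

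For patients still being scanned the gap is small. Scans are scheduled every two cycles, so it is at most about 56/30.4375 = 1.8 months if none is missed, and an ongoing arrow is fair. The trouble lies with patients whose assessments ended well before cutoff. The FAS is everyone who took a dose (SAP Section 8). Patients may withdraw at any time (protocol 9.3), those lost count as withdrawn (9.5), and required disease assessments stop when new anticancer therapy begins (9.4). All of these patients are in the figure, and the rule runs their bars through time in which nobody looked at the tumor. For a responder, the arrow states that the response continues.

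At stake is how durable the responses look. The DOR outputs are not in the final analysis, so a reader looking for durability is likely to turn to this figure, and the error can only lengthen bars.

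**Working it through.** The plan gives no figure to reproduce. The check applies the two rules to the same patients.

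**Inputs from the documents**
- SAP 9.8.3: PFS = [(last progression-free assessment − first dose) + 1]/30.4375. With study day 1 as the first dose (SAP 7.8), this is last-assessment day/30.4375. With no post-baseline scan, PFS is one day.
- SAP 9.8.2: censored DOR = [(last assessment − first CR/PR) + 1]/30.4375.
- Scan schedule (protocol Table 3.1, footnote l): Visit 5 (Day 29), then every two cycles, so the next is 29 + 56 = Day 85.
- Confirmation (SAP 9.8.1): a repeat assessment at least 4 weeks after response is first met. A PR on Day 29 and again on Day 85 qualifies, with response dated from Day 29.

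**Assumption**
- The SAP does not state a cutoff date. I use 6, 12 and 18 months after first dose, that is Days 183, 365 and 548.

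**Formula**
For an event-free patient whose scans stop early, bar length = cutoff day/30.4375, and

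excess = (cutoff day − last-assessment day)/30.4375.

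**Results, in months**

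| Last scan | PFS under SAP 9.8.3 | Excess, 6-month cutoff (bar 6.01) | Excess, 12-month cutoff (bar 11.99) | Excess, 18-month cutoff (bar 18.00) |
|---|---|---|---|---|
| None after baseline | 1/30.4375 = 0.03 | 5.98 | 11.96 | 17.97 |
| Day 29 | 29/30.4375 = 0.95 | 5.06 | 11.04 | 17.05 |
| Day 85 | 85/30.4375 = 2.79 | 3.22 | 9.20 | 15.21 |

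**The arrow**
Take a confirmed responder with first PR on Day 29 and last scan, still PR, on Day 85, who then leaves the study.
- DOR under SAP 9.8.2: (85 − 29 + 1)/30.4375 = 57/30.4375 = 1.87 months.
- Response as drawn, Day 29 to cutoff: 155/30.4375 = 5.09, 337/30.4375 = 11.07 or 520/30.4375 = 17.08 months, with the arrow on top.

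**Within the same report**
Listing 16.2.6-6, also in the final analysis, would give this patient PFS of 2.8 months, with the censoring date and reason. The figure would give 6, 12 or 18 months under the same name.

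**The case against.** The strongest reply is that this is a descriptive figure in an abbreviated, safety-focused report (SAP 7.2). It estimates nothing. ORR, PFS and OS are computed under their own rules, so a reader who infers that the PFS or DOR analyses are biased goes further than the documents allow. That stands: only the display is affected.

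Other outputs in the final analysis also let a reader recover the truth: the spider plot, Listing 16.2.6-4 with dated responses, and the PFS table, Kaplan-Meier figure and listing. This also stands, so the swimmer plot should not be called the main or only display of response over time. But needing a listing to correct a figure is a reason to mend the figure.

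The End of Treatment marker shows who is off drug. It does not show when tumor assessment ended. Patients who stop treatment without progression must go on being scanned (protocol 9.4), so the marker cannot separate someone still followed from someone lost.

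Two larger readings fail. A reader might add the 21-month accrual to the 18-month wait, get 39 months, and infer an overdraw of about 39 − 2.79 = 36 months. SAP 7.2 records that the study was terminated early in Part A, so that timeline no longer describes the final analysis. A reader might also suppose that a patient with a first PR on Day 85 who is lost days later gets the arrow. Without a repeat assessment that PR is unconfirmed: SAP Table 6, case 15, makes the best response SD, and SAP 9.8.2 counts as responders only those with a best response of CR or PR.

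Finally, the notes do not mention withdrawn or lost patients. Their inclusion follows from an unconditional rule applied to the FAS. The mock-up is not visible in the text available, so a legend or censor symbol in it cannot be checked.

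**Conclusion.** The contradiction is real, confined to the display, and worth correcting. Followed as written, the notes give every event-free patient whose scans ended before cutoff a bar longer than the SAP's PFS, by (cutoff − last assessment)/30.4375 months. They also give every such responder an arrow with no assessment behind it.

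Under the assumed cutoffs of 6 to 18 months, the excess is 3.2 to 15.2 months for a last scan on Day 85 and 6.0 to 18.0 months with no post-baseline scan. These are illustrations per patient, not predictions. The true size depends on the cutoff, which the SAP does not state, and on how many event-free patients left assessment early, which the documents do not say. SAP 9.8.2 itself makes its DOR intervals conditional on enough responder data, so the arrow may concern few patients. Early termination does not remove the issue: version 2.0 of the SAP was written to account for it and kept this figure in the final analysis.

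**What to change.** Change the notes for Figure 14.2-1.4.1 as follows:
- End the bar at the PFS event date, or for event-free patients at the SAP 9.8.3 censoring date, with a censor symbol.
- Show the ongoing-response arrow only for confirmed responders still under tumor assessment at cutoff whose last assessment shows no progression. A workable test is: not discontinued from the study, no new anticancer therapy, and last evaluable scan within one scheduled interval of cutoff (for example 8 weeks plus the 7-day window, 63 days).
- State the cutoff date in the SAP.

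The per-protocol and evaluable-set versions repeat this shell and would inherit the change. Listing 16.2.6-6 already carries the event or censoring date and the reason, so no new data are needed. The cost is a shell note and a few lines of code. Bars for patients still being followed will stop somewhat short of cutoff, and a footnote can explain this.

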**PROGRAMMING NOTES:**

[figure not shown]
- Repeat Figure 14.2-1.4.1
- Present data on Per Protocol Set.

Figure 14.2-1.4.3 – Swimmer Plot of Response Assessments  
Evaluable Analysis Set

**PROGRAMMING NOTES:**

- Repeat Figure 14.2-1.4.1
- Present data on Evaluable Analysis Set.

Figure 14.2-1.5.1 - Kaplan-Meier Estimate for Duration of Response  
Full Analysis Set

Program: (Program name.sas) (run on: DDMMYYYY HH:MM)

Filename: (Specify file name.rtf)

**PROGRAMMING NOTES:**

- X-axis – Label “Duration of Response (months)”
- Y-axis – Label “Event-free probability (%).”
- Legend: overall number of events, “Median Duration of Response” and 95% CI.
- Flag censored observations with ‘+’ and add legend.
- If the median time to event has not been reached, present as “Median (95% CI) NR (xx.x, xx.x)” [replacing xx.x with ‘-’ if there is no upper or lower confidence limit] and add footnote:  
NR=Median time not reached.
- For Part A, present all groups on the same figure but with different colors and separate figures for each group.

Figure 14.2-1.5.2 – Kaplan-Meier Estimate for Duration of Response  
Per Protocol Set

**PROGRAMMING NOTES:**

- Repeat Figure 14.2-1.5.1
- Present data on Per Protocol Set.

Figure 14.2-1.5.3 – Kaplan-Meier Estimate for Duration of Response  
Evaluable Analysis Set

**PROGRAMMING NOTES:**

- Repeat Figure 14.2-1.5.1
- Present data on Evaluable Analysis Set.

Figure 14.2-1.6.1 – Kaplan-Meier Estimate for Progression-Free survival (PFS)  
Full Analysis Set

**PROGRAMMING NOTES:**

- Replicate figure 14.2-1.5.1, replacing “Duration of Response” by “Progression Free Survival” in X-axis label and legend.

**Sponsor:** BioMed Valley Discoveries

**Protocol:** BVD-523-ABC

**Statistical Analysis Plan:**

2.0 / 09-Jun-2023

Figure 14.2-1.6.2 – Kaplan-Meier Estimate for Progression-Free survival (PFS)  
Per Protocol Set

**PROGRAMMING NOTES:**

- Replicate figure 14.2-1.5.1, replacing “Duration of Response” by “Progression Free Survival” in X-axis label and legend.
- Present data on Per Protocol Set.

Figure 14.2-1.6.3 – Kaplan-Meier Estimate for Progression-Free survival (PFS)  
Evaluable Analysis Set

**PROGRAMMING NOTES:**

- Replicate figure 14.2-1.5.1, replacing “Duration of Response” by “Progression Free Survival” in X-axis label and legend.
- Present data on Evaluable Analysis Set.

Figure 14.2-1.7.1 – Kaplan-Meier Estimate for Overall Survival  
Full Analysis Set

**PROGRAMMING NOTES:**

- Replicate figure 14.2-1.5.1, replacing “Duration of Response” by “Overall Survival” in X-axis label and legend.

Figure 14.2-1.7.2 – Kaplan-Meier Estimate for Overall Survival  
Per Protocol Set

**PROGRAMMING NOTES:**

- Replicate figure 14.2-1.5.1, replacing “Duration of Response” by “Overall Survival” in X-axis label and legend.
- Present data on Per Protocol Set.

Figure 14.2-1.7.3 – Kaplan-Meier Estimate for Overall Survival  
Evaluable Analysis Set

**PROGRAMMING NOTES:**

- Replicate figure 14.2-1.5.1, replacing “Duration of Response” by “Overall Survival” in X-axis label and legend.
- Present data on Evaluable Analysis Set.

**Sponsor:** BioMed Valley Discoveries

**Protocol:** BVD-523-ABC

**Statistical Analysis Plan:**

2.0 / 09-Jun-2023

BioMed Valley Discoveries  
Protocol: BVD-523-ABC ('Delivery' / 'Type') - Part X  
Data extraction date: DDMMYYYY

Page 1 of Y

Listing 16.2.1-1 - Patients informed consent  
All Patients Set

Group: Group 1

Subject ID	Age / Gender	Protocol Version	Main Informed Consent		Sample banking for future Biospecimen research consent		Optional End of Treatment Biopsy		Pregnancy and Pregnant Partner	
			Consent Obtained / Withdrawn?	Date Consent Obtained / Withdrawn	Consent Obtained / Withdrawn?	Date Consent Obtained / Withdrawn	Consent Obtained / Withdrawn?	Date Consent Obtained / Withdrawn	Consent Obtained?	Date Consent Obtained / Withdrawn
XXXXXX	XX/M	1.0	Yes / Yes	DDMMYYYY / DDMMYYYY	Yes	DDMMYYYY / DDMMYYYY	Yes	DDMMYYYY / DDMMYYYY	Yes	DDMMYYYY / DDMMYYYY
XXXXXX	XX/F	1.0	Yes / No	DDMMYYYY	Yes	DDMMYYYY	Yes	DDMMYYYY	Yes	DDMMYYYY
XXXXXX	XX/F	1.0	Yes / No	DDMMYYYY	Yes	DDMMYYYY	Yes	DDMMYYYY	Yes	DDMMYYYY
XXXXXX	XX/F	1.0	No / Yes	DDMMYYYY DDMMYYYY	No	DDMMYYYY	No	DDMMYYYY	No	DDMMYYYY
<cont.>										

Program: (Program name.sas) (run on: DDMMYYYY HH:MM)

Filename: (Specify file name.doc)

Listing 16.2.1-2 - Failed Inclusion and Exclusion Criteria  
All Patients Set

**Group: Group 1**

Subject ID	Age / Gender	Protocol Version	Failed Inclusion / Exclusion No.	Description
xxx-xx	xx/M	1.0	INCL01	xxxxxxxxxxxxxx
xxx-xx	xx/M	1.0	EXCL01	xxxxxxxxxxxxxx
xxx-xx	xx/M	1.0	EXCL02	xxxxxxxxxxxxxx
xxx-xx	xx/F	1.0	INCL02	xxxxxxxxxxxxxx

Program: (Program name.sas) (run on: DDMMYYYY HH:MM)

Filename: (Specify file name.rtf)

**PROGRAMMING NOTES:**

- List all failed Inclusion / Exclusion criteria as per eCRF.

**Sponsor:** BioMed Valley Discoveries

**Protocol:** BVD-523-ABC

**Statistical Analysis Plan:**

2.0 / 09-Jun-2023

BioMed Valley Discoveries  
Protocol: BVD-523-ABC ('Delivery' / 'Type') - Part X  
Data extraction date: DDMMYYYY

Page 1 of Y

Listing 16.2.1-3 - Patient Disposition  
All Patients Set

Group: Group 1

Subject ID	Age / Gender	Enrolled	Date of Assignment	Gene/ Codon/ Amino acid change	Completed Screening / Reason	Date of Screening Completion / Discontinuation	Eligible for inclusion?	Rescreened? / Previous patient number
xxx-xx	xx/M	Yes	DDMMYYYY	BRAF /D594 / Alanine A	Yes	DDMMYYYY	Yes	No
xxx-xx	xx/F	Yes	DDMMYYYY	MEK1/MAP2K1 / K601 /Arginine R	No / Physician Decision	DDMMYYYY	Yes	Yes /xxxxxxxx

Enrolled patients are patients that fullfill all selection criterion and included in the study to be dosed.  
Note: M=Male, F=Female.

Program: (Program name.sas) (run on: DDMMYYYY HH:MM)

Filename: (Specify file name.rtf)

BioMed Valley Discoveries  
Protocol: BVD-523-ABC ('Delivery' / 'Type') - Part X  
Data extraction date: DDMMYYYY

Page 2 of Y

Listing 16.2.1-3 - Patient Disposition  
All Patients Set

Group: Group 1

Subject ID	Age / Gender	Completed Treatment / Reason	Date of Treatment Discontinuation	Date of Last Study Dose	Completed Study / If no, reason	Date of Completion (Follow-up) / Discontinuation from Study
xxx-xx	xx/M	Yes	DDMMYYYY	DDMMYYYY	Yes	Yes
xxx-xx	xx/F	No/ Progressive Disease	DDMMYYYY	DDMMYYYY	No/ xxxxx	Yes

Note: M=Male, F=Female.

Program: (Program name.sas) (run on: DDMMYYYY HH:MM)

Filename: (Specify file name.rtf)

BioMed Valley Discoveries  
Protocol: BVD-523-ABC ('Delivery' / 'Type') - Part B  
Data extraction date: DDMMYYYY

Page 1 of Y

Listing 16.2.1-4 - Randomization  
Full Analysis Set

Subject ID	Randomization Number	Allocated treatment
xxx-xx	xxxxx	Ulixertinib - Group X
xxx-xx	xxxxx	Physician's Choice
xxx-xx	xxxxx	
xxx-xx	xxxxx	

Program: (Program name.sas) (run on: DDMMYYYY HH:MM)

Filename: (Specify file name.rtf)

**Sponsor:** BioMed Valley Discoveries

**Protocol:** BVD-523-ABC

**Statistical Analysis Plan:**

2.0 / 09-Jun-2023

BioMed Valley Discoveries  
 Protocol: BVD-523-ABC ('Delivery' / 'Type') - Part X  
 Data extraction date: DDMMYYYY

Page 1 of Y

Listing 16.2.2-1 - Analysis Sets  
 All Patients Set

**Part A**

**Group:** Group 1

Subject ID	Age / Gender	Full Analysis Set [a] All Patients Set [a]	Safety Analysis Set [c]	Per Protocol Analysis Set [d]	Evaluable Analysis Set [e]
xxx-xx	xx/M	Yes	Yes	Yes	Yes
xxx-xx	xx/F	Yes	Yes	Yes	Yes

Note: M=Male, F=Female.

[a] Patients who were enrolled regardless of whether they received the study drug or not.

[b] Patients who received at least 1 dose of the study drug.

[c] Patients who received at least 1 dose of the study drug.

[d] All patients from FAS who completed the study without any important protocol deviations.

[e] All patients from FAS who had the first efficacy evaluation on Study Day 29+3 and completed the study without any important protocol deviations.

Program: (Program name.sas) (run on: DDMMYYYY HH:MM)

Filename: (Specify file name.rtf)

Listing 16.2.3-1 - Protocol Deviations  
Full Analysis Set

Group: Group 1

Subject ID	Age / Gender	Deviation Category	Summary Term	Deviation Description	Important?	Exclusion from Analysis Sets
xxx-xx	xx/M	Inclusion Criteria	xxxxxxxxxxxxxx	xxxxxxxxxxxxxx	Non-Important	Safety Analysis Set
		...				
xxx-xx	xx/F	Study Assessments	xxxxxxxxxxxxxx	xxxxxxxxxxxxxx	Important	Full Analysis Set
		...				

Note: M=Male, F=Female.

Program: (Program name.sas) (run on: DDMMYYYY HH:MM)

Filename: (Specify file name.rtf)

